9.10.4. Overdose

An overdose is defined as a dose greater than the dose level evaluated in this study as described in Section 5. An overdose itself is not an AE unless it is an intentional overdose taken with possible suicidal/self-harming intent. Such overdoses must be reported regardless of sequelae. However, if the overdose results in clinical signs and symptoms, it requires an expedited reporting as if it is an SAE. In the case of a symptomatic overdose, the Investigator should use clinical judgment in treating the overdose and should inform the Sponsor immediately. The Investigators should refer to the relevant documents for detailed information regarding warnings, precautions, contraindications, AEs, and other significant data pertaining to the study drugs used in the study. Such document(s) may include, but not limited to, the IB for ALIS and approved product labeling for ARIKAYCE, or approved product labeling for azithromycin and ethambutol.

9.11. Follow-up of Adverse and Serious Adverse Events

After the initial AE/SAE report, the Investigator is required to proactively follow each subject at subsequent visits/contacts. All SAEs will be followed until resolution, stabilization, the event is otherwise explained, or the participant is lost to follow-up (as defined in [Section 4.2.3.1](#)). If the Investigator receives a report of any SAE, including a death, at any time after a subject has been discharged from the study, and the Investigator considers the event to be reasonably related to the study drugs or study participation, the Investigator must promptly notify the Sponsor.

9.12. Regulatory Aspects

The Sponsor has a legal responsibility to notify the FDA, National Competent Authorities and Central Ethics Committees of the European Union, and any other foreign regulatory competent agency, as well as all sites, about the safety of the drug. The Investigator has the responsibility to notify the local EC about SUSARs.

The Investigator(s)/institution(s) will permit study related monitoring, audits, IRB/EC review and regulatory inspection(s), providing direct access to source data/documents. Copies of the notification to the EC must be sent to the Sponsor.

10. STATISTICAL METHODS

Statistical analyses methods pertaining to validation of PRO will be included in VAP, and all other analyses will be described in SAP. The SAPs will include detailed description of methods and will be finalized prior to the database lock.

10.1. Sample Size and Power Considerations

Power and Sample Size Determination for the Validation Study

Cross-sectional validation will require baseline data from a maximum of 250 subjects to adequately power the planned MPMs. A total of 100 subjects will be enrolled in this study and will be used for this analysis. Additional baseline data from up to the first 150 subjects enrolled in a separate study will be used.

Longitudinal validation will require 100 subjects to adequately power the planned within-subject meaningful change methods.

The derivation of these sample sizes and the procedures used to compute power are described below.

Cross-sectional Validation Power and Sample Size

The estimated sample size required to conduct cross-sectional validation of the PRO endpoints within the NTM-MAC population was obtained from a power analysis assuming the PRO will be composed of 10 total items analyzed with 5 response categories each. This power procedure determines the sample size required to detect a domain specification that fits the data acceptably well. (Serrano and Iaconangelo, 2019; Serrano and Iaconangelo, 2017) The model fit statistic for which power was computed is the RMSEA. The RMSEA is the primary fit index used in modern psychometric methods for determining the optimal domain structure. This fit assessment is the logical test to power, as the modern psychometric methods require the largest sample sizes of all validation analyses. Therefore, adequately powering modern psychometric methods is key to validation study success. In addition, the precision of all validation analyses subsequent to modern psychometric methods rely on correct domain specification, which itself relies on the RMSEA.

For a 10-item questionnaire, approximately $n=250$ is required to achieve a power of 0.80 for the RMSEA-based test of acceptable MPM model fit. Therefore, a maximum of 250 subjects are planned for the study cross-sectional validation analyses. These subjects will contribute data at both screening and baseline for the purposes of estimated test-retest reliability as well.

Longitudinal validation analyses will be conducted on the subset of 100 subjects enrolled into this study.

Longitudinal Validation Power and Sample Size

An empirical power analysis simulation was conducted to evaluate the optimal sample size to adequately characterize culture converter anchor-based within-subject meaningful change in this study.

Inputs to the power analysis simulations were obtained from the MAC subset of the ALIS treated subjects in Insmed Study TR02-112, and simulation conditions considered reflected conservative variation around observed estimates (larger dispersion and smaller magnitudes of effect). The

following conditions were used to compute power: magnitudes of effect in change from baseline (6pt, 7pt, 8pt, 9pt, and 12pt change from baseline in converters, and 3 point change from baseline in non-converters); culture converter proportions (50%, 60%, and 70%); proportion data missing at random (MAR, 0%, 5%, 20%, 25%, and 30%); and sample size (n=100, n=120, and n=130). The polyserial correlation between simulated change from baseline in QOL-B respiratory domain and culture conversion varied around the observed estimate of 0.47, ranging from 0.3 to 0.6. Within each unique simulation condition r=1000 replications were generated. Empirical power was computed as the number of replications for which statistically significant differences between converters and non-converters in change from baseline in QOL-B respiratory domain score were observed. For example, if 900 replications demonstrated significant differences using the 2-sided test conducted at $\alpha=0.05$, then power was 90%.

A total sample size of 100 subjects (50 subject per treatment arm) will provide at least 80% power for detecting 7 points mean difference in QOL-B respiratory domain response at 1-month post treatment between subjects achieving culture conversion during the study and those who did not via ANOVA testing. This derivation assumes 50%, 60%, or 70% culture conversion rate, at least 40% polyserial correlation between culture conversion and QOL-B respiratory domain response, and missing data of 0%, 5%, or 20%.

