### Cross-sectional Validation Power and Sample Size

The estimated sample size required to conduct cross-sectional validation of the PRO endpoints within the NTM-MAC population was obtained from a power analysis assuming the PRO will be composed of 10 total items analyzed with 5 response categories each. This power procedure determines the sample size required to detect a domain specification that fits the data acceptably well ([Serrano and Iaconangelo, 2019\[10\]](#); [Serrano and Iaconangelo, 2017\[11\]](#)). The model fit statistic for which power was computed is the RMSEA. The RMSEA is the primary fit index used in modern psychometric methods for determining the optimal domain structure. This fit assessment is the logical test to power, as the modern psychometric methods require the largest sample sizes of all validation analyses. Therefore, adequately powering modern psychometric methods is key to validation study success. In addition, the precision of all validation analyses subsequent to modern psychometric methods rely on correct domain specification, which itself relies on the RMSEA.

For a 10-item questionnaire, approximately  $n=250$  is required to achieve a power of 0.80 for the RMSEA-based test of acceptable MPM model fit. Therefore, a maximum of 250

subjects are planned for the study cross-sectional validation analyses. These subjects will contribute data at both Screening and Baseline for the purposes of estimated test-retest reliability as well. Longitudinal validation analyses will be conducted on the subset of 100 subjects enrolled into this study.

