### **Longitudinal Validation Power and Sample Size**

An empirical power analysis simulation was conducted to evaluate the optimal sample size to adequately characterize culture converter anchor-based within-subject meaningful change in this study.

Inputs to the power analysis simulations were obtained from the MAC subset of the ALIS treated subjects in Insmmed Study TR02-112, and simulation conditions considered reflected conservative variation around observed estimates (larger dispersion and smaller magnitudes of effect). The following conditions were used to compute power: magnitudes of effect in change from baseline (6pt, 7pt, 8pt, 9pt, and 12pt change from baseline in converters, and 3 point change from baseline in non-converters); culture converter proportions (50%, 60%, and 70%); proportion data missing at random (MAR, 0%, 5%, 20%, 25%, and 30%); and sample size (n=100, n=120, and n=130). The polyserial correlation between simulated change from baseline in QOL-B respiratory domain and culture conversion varied around the observed estimate of 0.47, ranging from 0.3 to 0.6. Within each unique simulation condition r=1000 replications were generated. Empirical power was computed as the number of replications for which statistically significant differences between converters and non-converters in change from baseline in QOL-B respiratory domain score were observed. For example, if 900 replications demonstrated significant differences using the 2-sided test conducted at  $\alpha=0.05$ , then power was 90%.

A total sample size of 100 subjects (50 subjects per treatment arm) will provide at least 80% power for detecting 7 points mean difference in QOL-B respiratory domain response at 1-month post-treatment between subjects achieving culture conversion during the study and those who did not via ANOVA testing. This derivation assumes 50%, 60%, or 70% culture conversion rate, at least 40% polyserial correlation between culture conversion and QOL-B respiratory domain response, and missing data of 0%, 5%, or 20%.

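### The 80% longitudinal power is stated for a 7-point converter difference that was not simulated, and no SD is given; secondarily, the 0.80 RMSEA power assumes a 10-item, 5-category scale that matches neither instrument

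*Protocol*

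**What the plan says.** **Longitudinal sizing (Protocol 10.1, repeated in SAP 4.3.1).** The simulated effects were "6pt, 7pt, 8pt, 9pt, and 12pt change from baseline in converters, and 3 point change from baseline in non-converters". Inputs came from an earlier sponsor study, and "simulation conditions considered reflected conservative variation around observed estimates (larger dispersion and smaller magnitudes of effect"). The correlation between conversion and change in the QOL-B respiratory score "varied around the observed estimate of 0.47, ranging from 0.3 to 0.6". The conclusion is that 100 subjects "will provide at least 80% power for detecting 7 points mean difference in QOL-B respiratory domain response at 1-month post treatment" between converters and non-converters by ANOVA. It is conditional on 50%, 60% or 70% conversion, "at least 40% polyserial correlation between culture conversion and QOL-B respiratory domain response", and 0%, 5% or 20% missing data. The SAP makes the same claim: "will provide at least 80% power for detecting 7 points mean difference in QOL-B respiratory domain response". Neither document gives an SD.

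**Cross-sectional sizing (same sections).** About 250 subjects "is required to achieve a power of 0.80 for the RMSEA-based test of acceptable MPM model fit", "assuming the PRO will be composed of 10 total items analyzed with 5 response categories each". SAP 9.3.2.1 gives the QOL-B respiratory domain 9 items, each scored 1 to 4. SAP 9.3.3.1 gives PROMIS F-SF 7a 7 items on a 5-point scale. SAP 2 says the two produce separate scores, that items may be dropped, and that none will be added.

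**The concern.** These are the only power figures printed for the primary objective. A reader takes 7 points as the converter versus non-converter difference the study is sized to detect, yet no simulated pair of groups differs by 7. The most natural explanation is that the converters' own change was reported as if it were the between-group difference. Without the SD, the reader cannot tell whether the study is sized for 4 points or for 7.

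The RMSEA figure raises a smaller question of the same kind: 0.80 describes a questionnaire shape that neither instrument has. SAP 5.1 makes cross-sectional validation depend on the RMSEA fit test and relies on that test for adequate power, so a reader will take 0.80 as the power for these scales.

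**Working it through.** **1. The contrasts.** Converter change minus 3 gives 6−3=3, 7−3=4, 8−3=5, 9−3=6 and 12−3=9. Seven is not among them.

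**2. Reproducing the 80%.** Inputs from Protocol 10.1: N=100; conversion p = 0.5, 0.6, 0.7; polyserial r = 0.40; 0%, 5% or 20% missing, so n = 100, 95 or 80; two-sided test at 0.05.

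- Point-biserial correlation: r_pb = r·φ(z_p)/√(p(1−p))
- Standardised difference: d = r_pb / [√(1−r_pb²)·√(p(1−p))]
- Noncentrality: d·√(n·p(1−p)), noncentral t with n−2 df

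Example at p=0.5: r_pb = 0.40×0.3989/0.5 = 0.319, and d = 0.319/(0.948×0.5) = 0.674 (unrounded inputs).

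| p | r_pb | d | n=100 | n=95 | n=80 |
|---|---|---|---|---|---|
| 0.5 | 0.319 | 0.674 | 0.915 | 0.901 | 0.845 |
| 0.6 | 0.315 | 0.679 | 0.908 | 0.894 | 0.836 |
| 0.7 | 0.303 | 0.695 | 0.884 | 0.867 | 0.803 |

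The lowest cell is 0.803 (0.796 by simulation with 20,000 replications), which agrees with the stated 80%. With 25% missing and 70% conversion, power falls to 0.777, which fits the plan's stopping at 20%. No mean difference in points entered the calculation.

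**3. What the 80% means in points.** Implied within-group SD = difference/d.

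| p | SD if 4 points | SD if 7 points | Power for 4 points at the larger SD, n=100 | same, n=80 |
|---|---|---|---|---|
| 0.5 | 5.94 | 10.39 | 0.48 | 0.40 |
| 0.6 | 5.89 | 10.32 | 0.47 | 0.39 |
| 0.7 | 5.75 | 10.07 | 0.44 | 0.36 |

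The same 80% therefore describes either a 4-point contrast with SD about 5.8-5.9 or a 7-point contrast with SD about 10.1-10.4.

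**4. RMSEA (illustration only).** The plan prints no null RMSEA, alternative RMSEA, df or alpha, so its 0.80 cannot be reproduced. For example, 0.05 versus 0.08 at alpha 0.05 and n=250 gives 0.75 with df 35, but above 0.99 with df 710. To see how the 10-by-5 assumption matters, the unstated RMSEA value was solved so that a 10-item, 5-category scale has exactly 0.80 at n=250 (noncentral chi-square; exact-fit, close-fit and not-close-fit nulls), and then held fixed:

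| df convention | df: 10×5 / 9×4 / 7×5 / joint 16 items | 9×4 | 7×5 | Joint |
|---|---|---|---|---|
| Factor model | 35 / 27 / 14 / 103 | 0.70-0.71 | 0.46-0.50 | above 0.95 |
| Limited-information (M2), graded response | 710 / 315 / 329 / 1399 | 0.50-0.51 | 0.52-0.53 | above 0.95 |

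Under these assumptions, separate fits fall below 0.80 and a joint fit lies above it. The SAP and protocol do not say which is planned.

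**The case against.** **On the 7 points.** Seven lies between the simulated 6 and 9, and at a fixed SD power rises with the difference. If the 7-versus-3 condition is what was meant, at least 80% for a true 7 points is correct and even cautious. That stands as one possible reading, but it needs the small SD of about 5.8-5.9, which the documents do not give. A reader might therefore infer that the printed figure is safely conservative. Another might infer the opposite, that the study is underpowered because 4 points has only 36-48% power. Neither is supported, since each rests on an SD the plan does not state. Nor can the simulated correlation range of 0.3 to 0.6 settle which contrast was meant: 7 points falls outside that range only if the SD has already been chosen to fit 4 points. With SD about 10.1-10.4, 7 points corresponds to a correlation of 0.40, inside the range.

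**On consequence.** Protocol 10.5.2 uses conversion as an additional anchor beside the PGI-S, and no decision rule rests on the converter ANOVA. This stands and limits the importance of the point.

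**On RMSEA.** The 10-by-5 shape is disclosed as an assumption, made while the final item set was open. The Validation Analysis Plan, which was not supplied, may name the model and its hypotheses. Under SAP 5.1, progression depends on the fit found, not on the 0.80. All of this stands. A reader might infer that the RMSEA power is really below 0.80; that holds only if the scales are fitted separately and under the calibration above.

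**Conclusion.** The longitudinal statement is wrong as written: it names a 7-point between-group difference, and the simulation it summarises contains differences of 3, 4, 5, 6 and 9. The power is not shown to be wrong. It reproduces at 0.80-0.92 from the stated correlation, conversion rates, missing data and N. What is missing is the link to points: 4 at SD about 5.8-5.9, or 7 at SD about 10.1-10.4. These values rest on a polyserial correlation of exactly 0.40 and a two-group comparison with common variance.

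The RMSEA point is secondary. The 10-by-5 basis matches neither the 9-item, 4-category domain nor the 7-item, 5-category form, so 0.80 is not a power computed for either scale. Power is likely below 0.80 if they are fitted separately and above it if jointly. No size and no unconditional direction is claimed.

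**What to change.** 1. In SAP 4.3.1, replace the 7-point difference with the contrast actually simulated and give the SD used. If the 7-versus-3 condition is meant, this would read: a 7-point change in converters versus a 3-point change in non-converters, a 4-point difference. Alternatively, rerun the simulation for a true 7-point difference and report that power and SD. The first option costs one sentence and a value the sponsor already has; the second costs one rerun.
2. Rerun the sponsor's RMSEA power procedure at n=250 for the model or models named in the Validation Analysis Plan, and report the result in place of 0.80 with the null and alternative RMSEA and df. Otherwise, label 0.80 as a generic planning value for a 10-item, 5-category questionnaire. Separate powers at the 180 and 230 looks are optional.

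SAP 13 plans no further protocol amendment before unblinding, and SAP 2 gives the SAP precedence. The correction can therefore be made in the SAP, with the difference from the protocol explained in the CSR. N stays at 100, and no additional patients are needed.

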10.2. Analysis Sets

10.2.1. Intent-to-Treat Analysis Set

The ITT analysis set comprises all subjects who were randomized. This set will be analyzed using the treatment to which the subject was randomized.

10.2.2. Safety Analysis Set

The safety analysis set comprises all subjects who were randomized and received at least 1 dose of ALIS, ELC, AZI, or ETH.

10.2.3. Additional Analysis Sets

Additional analysis sets may be defined in the SAP as appropriate.

10.3. Data Handling Conventions

For all variables, only observed data from subjects will be used in the statistical analyses, ie, there is no plan to estimate missing data, unless otherwise stated. Detailed data imputation rules required for handling of missing events dates for safety data will be described in related data handling documents.

Unless otherwise stated, for subjects who discontinue ALIS or ELC and remain in the study for safety monitoring, data post-EOT will be programmatically relabeled to post-treatment visits; details will be included in SAP.

10.4. Multiplicity

All summaries will be descriptive without multiplicity adjustment. Confidence intervals for estimation of treatment differences will not be adjusted for multiplicity, p-values if provide will be nominal.

10.5. Study Population

The ITT analysis set will be used for all study population summaries unless otherwise stated. Summaries will be presented by treatment group and for all subjects based on the data available.

10.5.1. Study Population Disposition, Demographics and Baseline Characteristics

Subject demographic and baseline characteristics, including medical history, prior medications and therapies will be summarized using descriptive statistics.

For continuous variables, descriptive statistics (number [n], mean, standard deviation, median, minimum, and maximum) will be provided. For categorical variables, subject counts and percentages will be provided. Categories for missing data will be presented if appropriate.

The total number of subjects who were screened, randomized, completed the study, discontinued study drugs (including the reason), and withdrew consent from the study (including the reason) will be summarized by treatment group. The reason for discontinuing study drugs or withdrawal of consent from the study will be listed by subject.

Major protocol deviation will be summarized.

Assessments collected exclusively prior to therapy will be listed and summarized as appropriate (including data for FEV₁).

10.5.2. Primary Objective

The primary objective of this study is psychometric validation of PRO instruments.

Psychometric validation will consist of cross-sectional and longitudinal validation analyses. At Baseline, cross-sectional validation will consist of modern psychometric methods (exploratory factor analysis, item response theory models and corresponding assessments of local dependence and differential item functioning), internal consistency, concurrent validity, and known-groups validity. Longitudinal validation analyses conducted between Screening and Baseline will consist of test-retest reliability. The test-retest reliability population will consist of subjects reporting no change on PGI-S (respiratory for QOL-B and fatigue for PROMIS F-SF 7a) between Screening and Baseline. Longitudinal validation analyses conducted between Baseline and EOS (Month 7) will consist of the estimation of within-subject meaningful change. The within-subject meaningful change anchor definition will be derived from the change in PGI-S anchors (respiratory for QOL-B and fatigue for PROMIS F-SF 7a) between Baseline and EOS. In addition, culture converter status will be used as an additional anchor variable. Point estimates of within-subject meaningful change will consist of the mean change score conditioned on the PGI-S anchor definition. In addition, the median estimate will be examined in sensitivity analyses. Point estimates will be validated through the use of eCDFs and ePDFs.

10.5.3. Cross-sectional Validation

10.5.3.1. Modern Psychometric Methods

Evidence associated with these methods will be estimated at baseline. The main function of the modern psychometric methods employed will be the detection of any demonstrably irrelevant, redundant, or biased items. Full-information EFA and IRT models will be estimated in the service of this goal. Irrelevant items will be identified by item loadings (EFA) and slopes (IRT) approaching zero. Redundant items will be identified by local dependence statistics. Biased items will be detected through DIF assessments, including effect-size estimates to discriminate between statistically significant but meaningless DIF.

10.5.3.2. Internal Consistency

Internal consistency will be estimated at baseline via Cronbach's α and McDonald's ω , the latter being the unbiased model-based analog of α . Whereas α assumes item exchangeability, ω does not.

10.5.3.3. Concurrent Validity

Concurrent validity will be estimated based on Pearson correlations for scores between the QOL-B respiratory domain and PROMIS F-SF 7a and the following concurrent validators: EXACT and EXACT RS, SGRQ, and FACIT-Fatigue.

